11.5 Graft-versus-Host Disease

The proportion of subjects who develop chronic GvHD by Day +180 post-HSCT will be summarized.

The proportion of subjects with Grade 1, 2, 3, 4, 2-4, and 1-4 acute GvHD by Days +30, +100 and +180 post-HSCT will be summarized. Acute GvHD (defined separately for subjects \geq 45 kg or $<$ 45 kg) is defined using stages and grades according to Jacobsohn and Vogelsang ([Jacobsohn and Vogelsang 2007](#)), as shown in Table 5.

The following summary will be provided:

- Summary of GvHD

The following listings will be provided:

- Listing of acute GvHD
- Listing of chronic GvHD

Table 5. Staging and Grading of Acute Graft versus Host Disease

	Skin	Liver	Gut
		Total bilirubin (mg/dL)	Stool output (mL/day)
Stage			
0	No GvHD rash	<2	<500 or persistent nausea
1	Maculopapular rash $<25\%$ BSA	2-3	500-999 or 10-20 mL/kg/day for subjects <45 kg
2	Maculopapular rash 25%-50% BSA	3.1-6	1000-1500 or >20-35 mL/kg/day for subjects <45 kg
3	Maculopapular rash $>50\%$ BSA	6.1-15	>1500 or >35 mL/kg/day for subjects <45 kg
4	Generalized erythroderma plus bullous formation	>15	Severe abdominal pain with or without ileus
Grade	Skin	Liver	Gut
I	Stage 1-2	None	None
II	Stage 3 or	Stage 1 or	Stage 1
III	—	Stage 2-3 or	Stage 2-4
IV	Stage 4 or	Stage 4	—

GvHD: Graft-versus-host disease; BSA: Body surface area.
 Source: [Jacobsohn & Vogelsang 2007](#)

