The safety of defibrotide 25 mg/kg/day as prophylaxis has been demonstrated in children undergoing myeloablative conditioning considered to be at high risk of developing VOD (Corbacioglu et al. 2012). Incidences of AEs, serious adverse events (SAEs), and events leading to discontinuation were similar between the defibrotide and control groups (207 SAEs in 108 patients in the defibrotide group and 231 SAEs in 103 patients in the control group). Although the most common AE considered by the investigator to be related to defibrotide was hemorrhage, the cumulative incidence of hemorrhage was similar between groups (39 [22%] of 177 patients in the defibrotide group vs 37 [21%] of 176 patients in the control group;  $p=0.8176$ ). Overall, most fatal AEs were either neoplasms (12 [7%] of 177 patients in the defibrotide group and 14 [8%] of 176 patients in the control group) or infections (6 [3%] patients in the defibrotide group and 11 [6%] patients in the control group). In the intent-to-treat (ITT) population, patients who underwent allogeneic HSCT and who received defibrotide prophylaxis had a lower overall incidence of acute graft-versus-host disease (GvHD) (all grades) by Day +30 and +100 post-HSCT compared with those in the control group (Day +30 post-HSCT, 34% vs 53%  $p=0.004$ ; Day +100 post-HSCT, 47% vs 67%  $p=0.002$ ). A lower incidence of acute GvHD was also observed when grade 1 toxicity was excluded.

Defibrotide (JZP-381)  
Clinical Trial Protocol: 15-007 Version 4.0

Jazz Pharmaceuticals, Inc.  
20 August 2018

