### 4.1 Inclusion Criteria

Each patient must meet the following criteria to be enrolled in this study. Study treatment is defined as defibrotide prophylaxis in addition to BSC or BSC alone.

1. Patient must be above the age of 1 month as of Study Day 1 (as defined in [Section 3.1](#)).
2. Patient must be scheduled to undergo allogeneic (adults or pediatric patients) or autologous HSCT (pediatric patients only) and be at high risk or very high risk of developing VOD.
  - a. High-risk patients must meet both of the following criteria (i and ii):
    - i. Patient must be scheduled to receive myeloablative conditioning, defined as either of the following:
      - a. At least 2 alkylating agents (e.g., cyclophosphamide, busulfan, melphalan); the investigator must document in the medical chart that the conditioning regimen is considered to be myeloablative  
or
      - b. TBI (single dose of  $\geq 5$  Gy, or  $\geq 8$  Gy fractionated dose) and at least 1 alkylating agent, and
    - ii. Patient must meet at least 1 of the following criteria (a or b):
      - a. Has at least 1 hepatic-related risk factor, as defined by the European Society for Blood and Marrow Transplantation (EBMT) position statement (adapted and modified from [Mohty et al. 2015](#)), during screening as follows:
        - Transaminase level  $>2.5$  times the upper limit of normal (ULN) during screening or within 14 days prior to screening on a non-screening test if the test was performed as part of patient's routine standard of care
        - Serum total bilirubin level  $>1.5$  times the ULN during screening or within 14 days prior to screening on a non-screening test if the test was performed as part of patient's routine standard of care
        - Prior history of cirrhosis (with biopsy evidence)
        - Prior history of hepatic fibrosis (by histology or other diagnostic scoring system per institutional guidelines)
        - Prior history of viral hepatitis within 1 year before the start of study treatment as indicated by a positive test for any of the following:
          - hepatitis A virus (HAV) immunoglobulin M (IgM) (anti-HAV IgM)

- 
- hepatitis B virus (HBV) core immunoglobulin G (IgG) or IgM (anti-HBc IgG or anti-HBc IgM)
  - HBV surface antigen (HBsAg)
  - HBV DNA by polymerase chain reaction (PCR) or nucleic acid amplification testing (NAAT)
  - Hepatitis C virus (HCV) antibody (anti-HCV) and HCV RNA by PCR or NAAT

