### 9.8.1 Primary Efficacy Endpoint and Analysis

The primary efficacy analysis will be performed using the ITT population.

The primary efficacy endpoint is the VOD-free survival rate by Day +30 post-HSCT, as adjudicated by the independent EPAC. Kaplan-Meier estimates of the VOD-free survival rate by Day +30 post-HSCT will be presented for the 2 treatment arms and a stratified log rank test will be performed as the primary efficacy endpoint analysis to establish the treatment difference.

In addition, as a sensitivity analysis, the CMH test will be used to compare a composite binary endpoint of VOD free + alive at Day +30 post-HSCT between the 2 treatment arms, where the composite binary endpoint is defined by the proportion of patients who are VOD free and alive at Day +30 post-HSCT.

Additional sensitivity analyses for the primary efficacy endpoint will include but not limited to: the unstratified log rank test for the ITT population and the stratified log rank test using the mITT population.

Both the stratified log rank test and the CMH test will be performed by the 2 stratification variables for randomization - very high risk/high risk and pediatric ( $\leq 16$  years)/adults ( $> 16$  years).

The timing variable for the primary efficacy endpoint will be anchored at time of HSCT (time=0). It is anticipated that fewer than 2% of patients will not undergo HSCT in the ITT population. For those patients, time 0 is counted at randomization. The timing variable is

Defibrotide (JZP-381)  
Clinical Trial Protocol: 15-007 Version 4.0

Jazz Pharmaceuticals, Inc.  
20 August 2018

defined as the number of days from time 0 to the earlier of VOD or death by Day +30 post-HSCT. If a patient is not followed for 30 days, the censoring for that endpoint will be defined at the time of last available evaluation of VOD by EPAC. If a patient in BSC arm receives rescue treatment with defibrotide but VOD is not confirmed by EPAC then the patient will be censored at the time of rescue defibrotide initiation. Additional analysis based on other timing and censoring strategies will be considered and detailed in the SAP.

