## 9.14 Safety Endpoints and Analyses

Safety analyses will be conducted using the safety population.

In this study, the occurrence of VOD and the administration of rescue defibrotide represent a clinical landmark time point for safety. Therefore, for the safety analyses, 2 study phases are defined with respect to the administration of rescue defibrotide, as follows:

- Prophylaxis Phase – For the overall safety population, this phase is defined as the period between baseline and start date of rescue defibrotide, if applicable, or the period between baseline and Day +180 post-HSCT if no VOD occurred. (End date of Prophylaxis Phase=start date of rescue defibrotide – 1, or Day +180 post-HSCT if no VOD occurred)
- Treatment Phase – For the subset of patients in the safety population who developed VOD and received rescue defibrotide, this phase is defined as the period between start date of rescue defibrotide and Day +180 post-HSCT. (Start date of Treatment Phase=start date of rescue defibrotide)

Patients will be analyzed by study phase and by treatment received during the Prophylaxis Phase.

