6.4 Safety Analysis Set

The overall safety population will include all subjects randomized to the DP arm who receive at least 1 dose of defibrotide and all subjects randomized to the BSC arm. Subjects will be analyzed by the treatment they actually receive.

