11 SAFETY

Safety summaries will be provided by treatment arm and study phase based on the Safety Analysis Set.

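### GvHD proportions are planned on the whole Safety Analysis Set, including autologous recipients who are not at risk, so absolute rates and the absolute arm difference are understated

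*SAP*

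**What the plan says.** SAP 11.5 has one sentence for chronic GvHD, "The proportion of subjects who develop chronic GvHD by Day +180 post-HSCT will be summarized", and one for acute GvHD: "The proportion of subjects with Grade 1, 2, 3, 4, 2-4, and 1-4 acute GvHD by Days +30, +100 and +180 post-HSCT will be summarized". Neither names a denominator. The denominator comes from the opening of SAP 11: "Safety summaries will be provided by treatment arm and study phase based on the Safety Analysis Set". SAP 6.4 defines that set as "all subjects randomized to the DP arm who receive at least 1 dose of defibrotide and all subjects randomized to the BSC arm", with no condition on having been transplanted or on graft type. The protocol is no more restrictive. Section 9.14 says "Safety analyses will be conducted using the safety population", and 9.14.5 adds no filter.

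Protocol 4.1 admits both kinds of transplant: "Patient must be scheduled to undergo allogeneic (adults or pediatric patients) or autologous HSCT (pediatric patients only". Advanced-stage neuroblastoma is a named entry route. On patients who never reach transplant, Protocol 9.8.1 says "It is anticipated that fewer than 2% of patients will not undergo HSCT in the ITT population". SAP 8.2.3 gives such patients a Day +0 at randomization, which dates them but does not remove them.

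Comparing grade 2–4 acute GvHD and chronic GvHD between arms is a stated secondary objective (Protocol 2.2, SAP 4.2.2), and both appear among the other secondary endpoints in SAP 4.3.2.3.

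**The concern.** A proportion is informative when its denominator holds those who could have the event. Autologous recipients and untransplanted patients are not at risk of allogeneic GvHD, so counting them as GvHD-free lowers the displayed rate in each arm and narrows the absolute gap between arms.

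The plan follows the at-risk principle elsewhere. SAP 10.2.2.3 limits non-relapse mortality to patients with malignant disease, and SAP 11.6 censors untransplanted patients explicitly for engraftment. The protocol's own account of the earlier pediatric trial is allogeneic-only: "patients who underwent allogeneic HSCT and who received defibrotide prophylaxis had a lower overall incidence of acute graft-versus-host disease". SAP 11.5 would therefore report a different quantity from the one that the protocol cites, in a comparison that it lists as an objective.

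**Working it through.** The documents state no GvHD rate, power or sample size for this trial, so there is no planned figure to reproduce. The check asks how far the displayed numbers move.

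**Inputs**
- At-risk rates, DP vs control, borrowed from the earlier trial (Protocol 1.3; all grades, allogeneic): Day +30, 34% vs 53%; Day +100, 47% vs 67%.
- Not-at-risk share: not given. Assumed 5% to 20%.
- Untransplanted: 2%, the upper limit of the protocol's expectation.
- Planned size: 200 per arm (SAP 4.6).

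**1. Equal shares in both arms.** With not-at-risk share s, displayed rate = at-risk rate × (1 − s), and displayed difference = at-risk difference × (1 − s). The factor cancels from the risk ratio.

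| Day +30 | DP | BSC | Difference | Risk ratio |
|---|---|---|---|---|
| s = 0 | 34.0% | 53.0% | 19.0 points | 0.64 |
| s = 5% | 0.34 × 0.95 = 32.3% | 0.53 × 0.95 = 50.4% | 19 × 0.95 = 18.1 points | 0.64 |
| s = 20% | 0.34 × 0.80 = 27.2% | 0.53 × 0.80 = 42.4% | 19 × 0.80 = 15.2 points | 0.64 |

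At Day +100, with 20% autologous and 2% untransplanted, the at-risk fraction is 0.80 × 0.98 = 0.784. The display is 36.8% vs 52.5%. The difference falls from 20.0 to 15.7 points, and the risk ratio stays at 0.70.

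**2. Untransplanted patients alone.** At 2% in each arm, the Day +100 difference is 20.0 × 0.98 = 19.6 points, a loss of 0.4. The Safety Analysis Set keeps every randomized BSC patient but drops DP patients who were never dosed, so the two arms may not be equal here. If all 2% sat in BSC only, the difference would be 0.67 × 0.98 − 0.47 = 18.7 points. Autologous recipients drive the effect.

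**3. Unequal autologous shares.** The strata are risk, age and country; graft type is not one. With no true effect and a common at-risk rate r, the displayed difference (BSC − DP) is r × (share in DP − share in BSC). For an assumed 10% autologous share and 200 per arm, ignoring stratification, the SD of the between-arm difference in share is √(2 × 0.1 × 0.9 / 200) = 0.03. With r = 50% (assumed):
- a one-SD imbalance moves the GvHD difference by 0.5 × 3 = 1.5 points;
- a 1.96-SD imbalance (5.9 points of share) moves it by about 2.9 points.

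An extreme case shows that the direction can go either way. Using the Day +100 rates, 15% autologous in DP and 5% in BSC gives 0.67 × 0.95 − 0.47 × 0.85 = 23.7 points. The reverse gives 0.67 × 0.85 − 0.47 × 0.95 = 12.3 points. A 10-point gap in share is 10 / 3 = 3.3 SD, so this is not an expected outcome.

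**Limit of the calculation.** SAP 11 splits safety summaries by study phase. The figures above treat GvHD by a given day as one cumulative proportion, so the per-phase tables will not match them exactly.

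**The case against.** The strongest reply is that the denominator is inferred rather than stated. SAP 11.5 says only that proportions will be summarized; the Safety Analysis Set comes from a general sentence, and the table shells are a separate document (SAP 3) that could already carry a restriction. This does not remove the point. SAP 3 presents the SAP as a detailed and complete description, and nothing in either document limits the GvHD denominator.

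Other parts of the reply stand, and they block stronger readings that a reader might infer.

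- *That the treatment effect is diluted on every scale.* It is not. With equal shares the risk ratio is untouched.
- *That untransplanted patients matter much.* They are expected to be under 2%.
- *That imbalance in graft type would pass for a treatment effect.* Autologous HSCT is pediatric-only and neuroblastoma is a high-risk criterion, so the age and risk strata partly limit imbalance. SAP 9.4.2 also tabulates graft type by arm, so an imbalance would be visible.
- *That 5–20% is what the trial will show.* No share is given. Adults must be allogeneic, and most high-risk patients are predicted to be adult (Protocol 1.5), which limits it.
- *That 34% vs 53% describes the endpoint.* Those are all-grade acute rates. The objective concerns grades 2–4 and chronic GvHD, for which the documents give no rates.
- *That the change would make the results comparable with the earlier trial.* It removes one difference only. That trial enrolled only children, used other risk criteria and reported GvHD in its ITT population.

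**Conclusion.** The point holds in a limited form. Read as written, the plan counts patients not at risk of allogeneic GvHD as GvHD-free. Absolute rates and the absolute risk difference are understated by the not-at-risk share, while the risk ratio is unchanged if that share is equal between arms. Chance imbalance in graft type can shift the difference up or down by a few points.

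The size cannot be fixed from the documents. The shrinkage from 19 to about 18–15 points rests on an assumed 5–20% share, equal in both arms, and on all-grade rates from another population. SAP 11.5 plans a descriptive summary only, although SAP 4.3.2.3 lists GvHD among endpoints with nominal p-values. The impact is confined to a secondary safety objective. The primary and key secondary analyses, which concern VOD-free survival in the ITT set, do not depend on it.

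**What to change.** In SAP 11.5, define the main denominator for acute and chronic GvHD as Safety Analysis Set subjects who received an allogeneic HSCT, and show that n by arm in the table. Keep the all-subject version as a supportive table.

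The cost is one filter and one extra table. Graft type is already collected (Protocol 6.2.3) and summarized (SAP 9.4.2), so no new data are needed, and SAP 3 allows such decisions until database freeze. The small statistical drawback is that receiving the transplant is a post-randomization event, and in the DP arm it follows the start of defibrotide, so the filtered comparison is not strictly protected by randomization. With under 2% expected not to be transplanted, that risk should be small, and the supportive table lets a reader check it.

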11.6 Graft Failure and Time to Neutrophil and Platelet Engraftment

The incidence of neutrophil engraftment will be compared between the treatment arms. The date of neutrophil engraftment will be recorded on the eCRF and is defined as the first date after HSCT of an absolute neutrophil count $> 0.5 \times 10^9/L$ that is maintained for 3 consecutive days.

The definition of “absolute neutrophil count” includes both segmented neutrophils and “bands,” immature neutrophils.

The time to neutrophil engraftment is the number of days from the date of Day +0 post-HSCT to the date of neutrophil engraftment. Subjects with engraftment failure will be censored at the date of last contact or the Day+180 post-HSCT assessment date whichever is earlier. Subjects with ‘Never Below’ status will be censored at Day+1 post-HSCT. The remainder of the subjects who have not been considered as Engraftment/Failure/Never Below will be considered as ‘Undetermined’ and censored at the last neutrophil engraftment assessment date. For these undetermined subjects who have no assessment date or if the assessment date is prior to or on the HSCT date, they will be censored at Day+1 post-HSCT. If a subject does not undergo HSCT, the subject will be censored at the date of Day +1 post-HSCT.

This analysis will be repeated for platelet engraftment. The date of platelet engraftment will be recorded on the eCRF and is defined as the first date after HSCT of a platelet count $> 20 \times 10^9/L$ without a platelet transfusion in the preceding 7 days.

The following will be presented for neutrophil engraftment and platelet engraftment:

- The number of subjects by treatment group who achieved engraftment by Day +30 post-HSCT, Day +100 post-HSCT, and Day +180 post-HSCT.
- The number of subjects who were censored.
- The number of subjects who were ‘Never Below’.
- The number of subjects who did not have HSCT.
- The KM estimates of the engraftment rate (%) at Day +100 post-HSCT (95% CI).
- The KM estimate of median time to engraftment in days (95% CI).
- A KM plot will be presented up to Day +180 post-HSCT for each treatment arm. The number of subjects at risk will be displayed at 10-day intervals.

The following summaries will be provided:

- Analysis of time to neutrophil engraftment
- Analysis of time to platelet engraftment
- Summary of graft failure

The following figures will be provided:

- Figure of neutrophil engraftment
- Figure of platelet engraftment

The following listings will be provided displaying the dates for engraftment or graft failure:

- Listing of neutrophil and platelet engraftment
- Listing of engraftment status

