## 1.5 Justification for Selection of the Patient Population

In an unselected population, the incidence of VOD following HSCT has been estimated to be approximately 10% to 15% ([Coppell et al. 2010](#)). The incidence of VOD is estimated to be 20% to 25% in patients at high risk of VOD and 30% to 60% in patients at very high risk of VOD ([Table 3](#)). The assumed VOD-free survival at Day +30 post-HSCT considered in the design of this study takes into account a split between high risk and very high risk patients of 65% and 35%, respectively, which will be ensured at interim analyses, at the end of the study, and monitored throughout.

The all-cause mortality at this early time point (i.e., Day +30 post-HSCT) is not high; however, deaths do occur secondary to infection, GvHD, cardiopulmonary causes, relapse of underlying malignancy, and liver disease (primarily VOD). A recent publication noted a

Defibrotide (JZP-381)  
Clinical Trial Protocol: 15-007 Version 4.0

Jazz Pharmaceuticals, Inc.  
20 August 2018

decrease in all-cause mortality throughout the post-transplant course following myeloablative allogeneic HSCT; although Day +30 post-HSCT mortality was not separately reported, it would be estimated to be between 5% to 10% by Day +30 post-HSCT (Gooley et al. 2010). A separate study of intravenous versus oral busulfan for myeloablative HSCT reported 4% and 8% all-cause mortality by Day +30 post, respectively (Gupta et al. 2005). Given this, the incidence rate of VOD or death by Day +30 post-HSCT for this study (although it cannot be separately estimated by risk factor for VOD) would likely be 25% to 30% in patients at high risk of developing VOD and 33% to 63% in patients at very high risk of developing VOD.

The majority of patients in the high-risk population is predicted to be adult, whereas, patients in the very high-risk population are expected to be pediatric due to the presence of inherited diseases such as osteopetrosis and inherited hemophagocytic syndromes. There will however be adults in the very high-risk population (those receiving the ozogamicin antibody conjugates) and pediatric patients in the high-risk population (those with pre-existing liver disease and neuroblastoma).

**Table 3 Estimated Risk of Developing Veno-Occlusive Disease by Day +30 Following Hematopoietic Stem Cell Transplant in High-Risk and Very High-Risk Patient Populations**

Patient Subset	Characteristics	Estimated Incidence of VOD by Day +30 post-HSCT	Reference

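### SAP 11.6 censors deaths before engraftment in a Kaplan-Meier analysis, so the Day +100 engraftment rate is overstated, by an amount the documents do not fix

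*SAP*

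**What the plan says.** SAP 11.6 plans a comparison of engraftment between the arms and places subjects in the following groups:

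- **Engraftment:** the event. For neutrophils it is a count above the threshold "that is maintained for 3 consecutive days". For platelets it is a count above the threshold "without a platelet transfusion in the preceding 7 days".
- **Engraftment failure:** "Subjects with engraftment failure will be censored at the date of last contact or the Day+180 post-HSCT assessment date whichever is earlier".
- **Never Below, and no HSCT:** censored at Day +1.
- **Undetermined:** everyone left over, "censored at the last neutrophil engraftment assessment date", or at Day +1 if there is no assessment after HSCT.

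"This analysis will be repeated for platelet engraftment".

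The outputs include "The KM estimates of the engraftment rate (%) at Day +100 post-HSCT (95% CI", the Kaplan-Meier median with its interval, and a Kaplan-Meier plot. The same list also has "The number of subjects by treatment group who achieved engraftment by Day +30 post-HSCT, Day +100 post-HSCT, and Day +180 post-HSCT".

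Protocol 9.14.6 likewise plans Kaplan-Meier curves. Among the summary statistics it asks for the percentage of patients who engraft by Day +100. Neither section mentions death or a competing-risk method. The SAP reference list does contain the K-sample test for cumulative incidence (Gray's test), but no section of the SAP uses it.

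**The concern.** A patient who dies before engrafting can never engraft. Censoring tells the Kaplan-Meier estimator the opposite: it shares that patient's probability among those still at risk, as if the patient would have engrafted at the survivors' pace. The result is an engraftment probability for a setting in which nobody dies first. It is not the share of transplanted patients who engraft by Day +100, which is what Protocol 9.14.6 asks for and what most readers will take the rate to mean.

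Early death is not rare in this population. For all-cause mortality after myeloablative allogeneic HSCT, Protocol 1.5 says "it would be estimated to be between 5% to 10% by Day +30 post-HSCT", and it cites 4% and 8% from a second study.

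Two things are at stake. First, the rate, its interval, the median and the plot would all describe the wrong quantity, and the rate would disagree without explanation with the crude Day +100 count in the same table. Second, if early mortality differs by arm, the arm with more early deaths has its engraftment rate raised more.

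**Working it through.** **Direction.** The classes are exhaustive and death is not an event in any of them. A death before engraftment is therefore censored, at last contact (failure) or at the last assessment (undetermined). Once one such death precedes later engraftments, 1 − KM exceeds the cumulative incidence. This step needs no numerical assumption.

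**Size.** The documents state no engraftment rate, so there is no figure of the plan's to reproduce.

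Inputs:
- Deaths, p = 5% and 10% (Protocol 1.5, all-cause by Day +30).
- Assumed, not in the documents: 97% eventually engraft; lognormal engraftment times with log-SD 0.5; medians as shown in the table; deaths independent of engraftment.

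Let F(t) be the engraftment distribution in the absence of death and G(t) the probability of being alive at t.

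- KM estimates F(100).
- Cumulative incidence = ∫ G(t) dF(t) over Days 0 to 100.
- Gap = ∫ [1 − G(t)] dF(t).

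With deaths uniform over Days 0 to 30, 1 − G(t) = p × min(t/30, 1), so the gap is p × ∫ min(t/30, 1) dF(t). The integral is 0.66 for a median of Day 20 and 0.79 for Day 28. Hence:
- Median Day 20: 0.05 × 0.66 = 3.3 points and 0.10 × 0.66 = 6.6 points.
- Median Day 28: 0.05 × 0.79 = 4.0 points and 0.10 × 0.79 = 7.9 points.

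With the same deaths uniform over Days 5 to 60, the corresponding integrals are 0.31 and 0.45.

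| Deaths | Median (day) | KM | Cumulative incidence, p = 5% / 10% | Gap in points, p = 5% / 10% |
|---|---|---|---|---|
| Days 0–30 | 14 | 97.0% | 94.5% / 92.0% | 2.5 / 5.0 |
| Days 0–30 | 20 | 96.9% | 93.6% / 90.4% | 3.3 / 6.6 |
| Days 0–30 | 28 | 96.5% | 92.5% / 88.5% | 4.0 / 7.9 |
| Days 5–60 | 14 | 97.0% | 96.0% / 95.1% | 1.0 / 1.9 |
| Days 5–60 | 20 | 96.9% | 95.4% / 93.9% | 1.5 / 3.1 |
| Days 5–60 | 28 | 96.5% | 94.2% / 92.0% | 2.2 / 4.5 |

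Gaps were computed before rounding. For medians of Day 20 to 28, varying the log-SD from 0.35 to 0.7 gives 3.2 to 8.3 points (deaths over Days 0–30) and 1.4 to 4.5 points (Days 5–60). Because the shapes are assumed, I round these to about 3 to 9 and about 1.5 to 5.

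**Check against the SAP's own censoring.** Simulating with deaths censored at the last weekly assessment (deaths over Days 0–30, median Day 28) gives KM 96.5% against 92.5% actually engrafted at p = 5%, and 96.6% against 88.6% at p = 10%. These match the table.

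**Neutrophils and platelets.** The gap grows with the median, so it is larger for whichever lineage engrafts later. With equal medians the two nearly coincide: at a median of 18 days, 10% Day +30 mortality and a constant death hazard, it is 6.3 points with the neutrophil spread (log-SD 0.35) and 6.6 with the platelet spread (0.5).

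**Between arms.** If both arms share the same engraftment times and the same mortality, both rates rise equally. If mortality is 5% in one arm and 10% in the other (median Day 28, deaths over Days 0–30), KM shows 96.5% in both, while the proportions that engraft are 92.5% and 88.5%.

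**The case against.** The strongest reply is that the report already holds what a careful reader needs. SAP 11.6 tabulates the number engrafted by Day +100, which divided by the arm total is close to the quantity wanted. It also gives the numbers censored and a graft-failure summary. Early deaths enter the primary composite (SAP 10.1), VOD-free survival to Days +100 and +180 (10.2.1, 10.2.2.2), non-relapse mortality (10.2.2.3) and adverse events leading to death (11.2). SAP 11.6 names no test, hazard ratio or p-value for engraftment, and the endpoint lies outside the multiplicity control.

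All of this stands, and it limits the consequence. It does not correct the rate: the only Day +100 figure with an interval, the median and the plot all come from Kaplan-Meier.

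Three stronger readings are tempting, and the documents do not support them.

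- **That the plan hides early deaths.** The Kaplan-Meier rate taken alone leaves them out; the report as a whole does not.
- **That the overstatement reaches 12 points or more.** A 12-point gap needs 15% of patients to die before platelet engraftment. That is above the Protocol's 5% to 10%, which is all-cause and includes deaths after engraftment. Figures near 14 points need a platelet median of Day 45 and a constant death hazard to Day +100. With 10% dead by Day +30, that hazard implies 1 − 0.9^(100/30), about 30%, dead by Day +100.
- **That platelets are necessarily worse affected.** The seven-day transfusion-free rule makes later platelet engraftment plausible, but neither document gives engraftment times.

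Nor does the SAP say how a death before engraftment is classified. Either class leads to censoring, so the conclusion is unaffected.

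**Conclusion.** The point holds. As written, SAP 11.6 censors deaths before engraftment. Its Kaplan-Meier rate at Day +100 therefore overstates engraftment, its interval surrounds that overstated value, and its median and plot show engraftment as faster and more complete than patients will experience. The rate will also disagree with the crude count beside it and with the percentage requested in Protocol 9.14.6.

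The size is conditional. It is about 3 to 9 points if 5% to 10% die by Day +30, independently of engraftment, with a platelet median of Day 20 to 28. It is about 1.5 to 5 points if the same deaths are spread over Days 5 to 60. It is larger for platelets only if they engraft later than neutrophils. If slow engraftment and early death go together, independence fails and the gap would be wider than these figures.

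The comparison between arms is affected mainly if early mortality differs by arm. This is worth correcting before database freeze, but it does not touch the primary or key secondary inference.

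**What to change.** In SAP 11.6, replace the Kaplan-Meier rate and plot with the cumulative incidence of engraftment by arm, for neutrophils and platelets separately. Treat death without engraftment as a competing event at the date of death, and keep graft failure as not engrafted. Report the Day +100 value with its 95% confidence interval, and state explicitly how a death before engraftment is classified. If a p-value is wanted, Gray's test is already in the SAP reference list. Kaplan-Meier may stay as a secondary display, labelled as censoring deaths.

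The cost is minor SAP wording and programming with standard software. No new data are needed, because survival status is already collected at the scheduled visits. The reported engraftment rate will be slightly lower.
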